6.4.15. Phase 2 and Phase 2 Extension Unscheduled Visit

Unscheduled visits may be conducted at any time during Phase 2 by the investigator if clinically indicated for the care of the patient.

An unscheduled visit may include any of the protocol required assessments listed in [Section 8: Phase 2 Assessments](#). The exact assessments conducted at the unscheduled visit will be specified by the investigator and recorded in the CRF. Additional tests and procedures may

Investigational Product: IMU-131
Protocol Identifier: IMU.ACS.001
Protocol Version: Protocol Global Amendment #5, 27 September 2023

be performed at the unscheduled visit for the clinical care of the patient after discussion with, and agreement of, the medical monitor.

6.5. Patient Withdrawal

6.5.1. Main discontinuation criteria

Patients will discontinue study treatment and complete the study according to the study protocol when there is documented evidence of disease progression according to RECIST 1.1 response criteria or if unacceptable toxicity occurs. Patients may discontinue study treatment and be withdrawn from the study prematurely based on symptomatic clinical disease progression without documented radiographic evidence only after discussion with the Sponsor/medical monitor.

6.5.2. Contraindications to repeated vaccination

If any of the following adverse events arise during the study they constitute contraindications to further administration of IMU-131, and patients should discontinue IMU-131 treatment permanently and be withdrawn from the study immediately, with appropriate safety follow-up by the investigator until resolution of the event, as with any adverse event (see [Section 9: Adverse Event Reporting](#)):

- Anaphylactic reaction following the administration of vaccine(s).
- Any clinically relevant immunosuppressive or immuno-deficient condition.

The following events constitute contraindications to administration of IMU-131. If an adverse event, the event must be reported and the patient followed as with any adverse event. Withdrawal of patients experiencing the following events is at the discretion of the investigator as indicated below:

- Acute illness at the time of vaccination. Acute illness is defined as the presence of a moderate or severe illness with or without fever. All vaccines can be administered to persons with a minor illness such as diarrhea, mild upper respiratory infection with or without low-grade febrile illness, i.e., temperature $<38^{\circ}\text{C}$. Withdrawal is at the discretion of the investigator if acute illness will not resolve in sufficient time to allow for vaccination schedule to continue.
- Temperature $\geq 38^{\circ}\text{C}$ at the time of vaccination. Withdrawal is at the discretion of the investigator if raised temperature will not resolve in sufficient time to allow for vaccination schedule to continue.

6.5.3. Additional Discontinuation Criteria

Patients must discontinue from the study if any of the following additional criteria are met:

- The patient requests discontinuation from the study;
- The Sponsor stops the study;
- The Sponsor stops the patient's participation in the study;
- The patient becomes pregnant during the study period.

Investigational Product: IMU-131
Protocol Identifier: IMU.ACS.001
Protocol Version: Protocol Global Amendment #5, 27 September 2023

Patients may withdraw from the study at any time at their own request, or they may be withdrawn at any time at the discretion of the investigator or Sponsor for safety or behavioral reasons, or the inability of the patient to comply with the protocol required schedule of study visits or procedures at a given study site.

If a patient does not return for a scheduled visit, every effort should be made to contact the patient. In any circumstance, every effort should be made to document patient outcome, if possible. The investigator should inquire about the reason for withdrawal, request the patient to return for a final visit, if applicable, and follow-up with the patient regarding any unresolved adverse events (AEs).

If the patient withdraws from the study, and also withdraws consent for disclosure of future information, no further evaluations should be performed, and no additional data should be collected. The Sponsor may retain and continue to use any data collected before such withdrawal of consent.

7. PHASE 1B ASSESSMENTS

Every effort should be made to ensure that protocol required tests and procedures are completed as described.

7.1. Phase 1b Physical Examination (Screening, Days 0, 14, 35, 56, 77, 98, LTM visits)

The physical examination will include an evaluation of body systems (e.g. cardiovascular, gastrointestinal, neurological, head and neck, respiratory, dermatology). Evaluation for pre-existing condition that might exclude the patient from eligibility or could interfere with the patient's participation and compliance with the protocol should be performed at Screening.

7.2. Phase 1b Height, Weight and Vital Signs (Screening, Days 0, 14, 35, 56, 77, 98, LTM visits)

Body height (at screening visit only), weight, and vital signs (blood pressure, pulse and temperature) will be measured.

7.3. Phase 1b Radiographic Assessment (Screening, Days 56, 98, LTM visits)

For all patients, a radiographic assessment will be performed at Screening (for inclusion criteria assessment), and at Day 56, Day 98 and at long term maintenance visits until disease progression.

Computed Tomography (CT) scan of the chest abdomen and pelvis with contrast should be performed. MRI of the abdomen and pelvis with contrast and non-contrast CT chest may be done in patients with iodine contrast dye allergy or if lesions cannot be visualized on CT scan.

Radiographic assessments must be performed within +/- 2 weeks of the planned visit date. Additional radiographic assessment may be performed as part of a Phase 1b Unscheduled

Investigational Product: IMU-131
Protocol Identifier: IMU.ACS.001
Protocol Version: Protocol Global Amendment #5, 27 September 2023

Visit ([Section 6.2.8](#)) at the discretion of the investigator as clinically indicated. Assessment of the tumor will include evaluation according to the RECIST 1.1.

7.4. Phase 1b Cardiac Assessment (Screening, Day 56)

Cardiac assessment of suitability for inclusion in the study and on Day 56 will be performed by the study investigator and be based on assessment of medical history, physical examination, 12-lead ECG results and evaluation of left ventricular ejection fraction (LVEF) by echocardiography or MUGA scan. Cardiology consult may be sought by the investigator if required to confirm suitability for inclusion in the study.

7.5. Phase 1b Laboratory Assessments

Hematology and serum chemistry analyses will be performed by an accredited central laboratory. Immunological analysis will be performed by an accredited specialist immunology laboratory.

Central laboratory results should be reviewed by the principal investigator (PI) or another qualified study staff member as soon as received. Subject management is dependent upon close review of the laboratory data.

Unscheduled and repeat laboratory tests will also be performed by the central laboratory. However, if the turnaround time from the central laboratory is not sufficiently rapid for clinical management of the subject, local laboratory test results may be used to make the necessary clinical judgments.

A Central Laboratory Manual with instructions on specimen collection, processing, storing, and shipping will be provided to all participating sites.

7.5.1. Phase 1b Safety Laboratory Assessments (Screening, Days 0, 14, 35, 56, 77, 98, LTM visits)

Blood samples of approximately 10 mL in total for the assessment of hematological and serum chemistry parameters will be collected and processed in accordance with the central laboratory study manual.

All hematology and serum chemistry samples will be submitted by the Investigator to the certified central laboratory for analysis. Blood samples for hematology and serum chemistry will be prepared using standard procedures.

Safety laboratory panels are defined as follows:

Human immunodeficiency virus (HIV 1/2 antibodies), hepatitis B (HBsAg reactive) and hepatitis C (HCV ribonucleic acid [RNA] qualitative) (at screening only).

Hematology: Hematology to include CBC, including RBC count, hemoglobin, hematocrit, reticulocyte count, WBC count with differential (neutrophils, bands, eosinophils, basophils, lymphocytes, monocytes, and other cells), platelet count, C-reactive protein (CRP), IL-1, IL-6, IL8, TNF-a, CXCL-9 and CXCL-10.

Investigational Product: IMU-131
Protocol Identifier: IMU.ACS.001
Protocol Version: Protocol Global Amendment #5, 27 September 2023

Serum Chemistry: BUN or urea, creatinine, sodium, chloride, potassium, magnesium, bicarbonate, calcium, phosphorus, total protein, albumin, alkaline phosphatase, glucose, total bilirubin, direct and indirect bilirubin, lactate dehydrogenase (LDH), cholesterol, uric acid, triglyceride levels, gamma glutamyl transpeptidase (GGT), AST, and ALT.

Abnormalities in clinical laboratory tests that are considered clinically significant by the investigator will be recorded on the laboratory CRF page. If abnormal laboratory results are also considered an adverse event, then a corresponding AE CRF will also be completed. If values after the first dose meet criteria defining them as serious, they must be reported as SAEs (see [Section 9.12.1: Serious Adverse Event Reporting Requirements](#)).

7.5.2. Phase 1b Immunologic Assessments (Screening, Days 0, 14, 35, 56, 77, 98, LTM visits)

Prior to each vaccination a 1 x 8 mL whole blood sample for humoral immunity will be obtained from the patient at Days 0, 14, 35, 56, 77, 98 and at LTM visits. Additionally, on Days 0, 56 and at each LTM visit, 5 x 8 mL heparinized blood samples will be collected for PBMC isolation and analysis of cellular parameters.

All blood samples for immunological assessment will be collected and processed at the study site according to the Central Laboratory Manual. These immunological blood samples will be collected by, and stored at, the central laboratory before bulk shipment to the specialist immunology laboratory at the [REDACTED] [REDACTED] for analysis.

7.5.3. Phase 1b HER2/neu overexpression (Screening)

Confirmation of HER2/neu overexpression is required for inclusion in this study. However, patients with IHC HER2 ++ expression without confirmation of overexpression by fluorescent *in situ* hybridization [FISH] brightfield double *in situ* hybridization [BDISH] or chromogenic *in situ* hybridization [CISH]) may be included in Phase 1b with agreement of Imugene Limited.

A previous pathology result confirming HER2/neu overexpression is acceptable. If analysis of a tumor biopsy is required for confirmation of HER2/neu overexpression then this may be achieved via analysis of a fresh or archived tissue sample. Results are to be entered into the respective CRF.

If a biopsy sample is used to determine HER2/neu overexpression then analysis of intra-tumor T cells for CD8+, CD4+, Th1, Th2, Tregs (Foxp3+ CD25+) will also be performed if these analyses are available at the pathology lab conducting HER2/neu overexpression analysis.

HER2/neu analysis will be conducted at each center's local pathology laboratory by immunohistochemistry (IHC) and fluorescent *in situ* hybridization [FISH] or chromogenic *in situ* hybridization [CISH] if IHC result is equivocal.

Using the IHC method an unequivocal result of HER2 overexpression is defined as HER2 +++, an equivocal result is defined as HER2 ++, and a negative result is defined as HER2 +. If equivocal result (IHC HER2++) then additional analysis via FISH or CISH will be

Investigational Product: IMU-131
Protocol Identifier: IMU.ACS.001
Protocol Version: Protocol Global Amendment #5, 27 September 2023

conducted for confirmation of HER2 overexpression. The definition of FISH or CISH positivity in gastric or gastro-esophageal junction cancer is a HER2: chromosome 17 ratio of ≥ 2.0 .

7.5.4. Phase 1b ECOG performance grade (Screening)

The ECOG performance grade for screening evaluation should be determined using the criteria defined in [Appendix 3](#): ECOG Performance Status Scale.

7.6. Phase 1b Vaccination site evaluation (Days 2, 16, 37)

The purpose of vaccination site evaluation is to determine the nature and frequency of local/vaccination site reactions. The vaccination site should be evaluated for local effects of the vaccine injection including pain, tenderness, erythema/redness and swelling/induration (see [Section 9.7.1](#) Local (injection site) Adverse Event Intensity for further details). All local vaccination site effects are to be reported in the CRF and graded according to [Table 4](#): Grading of Local Adverse Event Intensity presented in [Section 9.7.1](#).

Photographs will be taken during vaccination site evaluation if there are visible local injection site reactions.

7.7. Phase 1b Pregnancy Test (Screening, Days 0, 14, 35, 98, LTM visits)

For female patients of childbearing potential, a urine pregnancy test, with sensitivity of at least 25 mIU/mL, will be performed immediately before administration of each vaccine dose. A negative pregnancy test result is required before the patient may receive the investigational product. If urine pregnancy test is positive then confirmation of pregnancy will be by BHCG blood test. If BHCG blood test is negative then vaccination schedule may resume. Pregnancy tests may also be repeated as per request of IRB/IECs or if required by local regulations.

8. PHASE 2 AND PHASE 2 EXTENSION ASSESSMENTS

Every effort should be made to ensure that protocol required tests and procedures are completed as described.

8.1. Assessments via Telemedicine

Telemedicine uses advanced telecommunication technologies to exchange health information and provide health care services across geographic, social, and other barriers. Where circumstances allow, and where additional flexibility is required due to restricted patient access to the study clinic or personnel, telemedicine technology may be used to collect study data to supplement study assessments. For example, visits may be conducted over several days within each visit window, with suitable assessments being completed using telemedicine technology with the remaining assessments being completed during a physical clinic visit. Examples of study assessments which may be completed using telemedicine technology include documenting concomitant treatments and adverse events, ECOG performance grade, and survival follow-up.

Investigational Product: IMU-131
Protocol Identifier: IMU.ACS.001
Protocol Version: Protocol Global Amendment #5, 27 September 2023

8.2. Phase 2 and Phase 2 Extension Physical Examination (Screening, Baseline, Days 21, 42, 63, 84, 105, 126 then every 42 days and EoT visit)

The physical examination will include an evaluation of body systems (e.g. cardiovascular, gastrointestinal, neurological, head and neck, respiratory, dermatology). After the Baseline physical examination, a symptom-directed physical examination is allowed at subsequent visits at the investigator's discretion.

8.3. Phase 2 and Phase 2 Extension Height, Weight, Vital Signs, Concomitant Medications, Concomitant Procedures and Adverse Events (at each study visit, excluding post-treatment follow-up visits)

Body height (at screening visit only), weight, and vital signs (blood pressure, pulse and temperature) will be measured and concomitant medications, concomitant procedures and adverse events will be documented.

8.4. Phase 2 and Phase 2 Extension Radiographic Assessment (Baseline, Days 42, 84, 126 then every 42 days)

For all patients a radiographic assessment will be performed at Baseline (assessment allowed up to 14 days before Baseline Visit), Days 42, 84, 126 then every 42 days until disease progression. Assessment of the tumor will include evaluation according to RECIST 1.1.

In the Phase 2 extension, a repeat scan may be performed as an unscheduled visit at the investigator's discretion to confirm progression 4-6 weeks after the date of the original scan indicating progression. If progression is confirmed the original date of progression will be used for disease assessment.

8.5. Phase 2 and Phase 2 Extension Cardiac Assessment (Screening, Day 84 then every 84 days and EoT visit)

Cardiac assessment to be performed at Screening, on Day 84 then every 84 days and at EoT visit. It will be performed by the study investigator and be based on assessment of medical history, physical examination, 12-lead ECG results and evaluation of left ventricular ejection fraction (LVEF) by echocardiography or MUGA scan.

8.6. Phase 2 and Phase 2 Extension Laboratory Assessments

Hematology and serum chemistry analyses will be performed by an accredited local laboratory. Serum predication markers of tumor progression and intra-tumor T cell and biomarker analysis will be performed by an accredited central laboratory. Humoral and cellular immunological analysis will be performed by an accredited specialist central immunology laboratory.

Unused blood /serum and/or tissue samples collected during the study from patients who have signed an appropriate informed consent form may be stored and used for future research. The coded samples may be stored up to 15 years after the clinical study ends. A patient may contact the investigator to have their unused samples destroyed at any time

Investigational Product: IMU-131
Protocol Identifier: IMU.ACS.001
Protocol Version: Protocol Global Amendment #5, 27 September 2023

during the storage period. Results from the future use studies will not be shared with patients.

1) Safety Laboratory Assessments (Screening, Baseline, Days 21, 42, 63, 84, 105, 126 then every 42 days and EoT visit)

Blood samples of approximately 10 mL per visit for the assessment of hematological and serum chemistry parameters will be collected and processed in accordance with local laboratory procedures and reference ranges.

Safety laboratory panels are defined as follows:

Human immunodeficiency virus (HIV 1/2 antibodies), hepatitis B (HBsAg reactive) and hepatitis C (HCV ribonucleic acid [RNA] qualitative) (at screening only).

Hematology: Hematology to include CBC, including RBC count, hemoglobin, hematocrit, reticulocyte count, WBC count with differential (neutrophils, bands, eosinophils, basophils, lymphocytes, monocytes, and other cells), platelet count, and C-reactive protein (CRP).

Serum Chemistry: BUN or urea, creatinine, sodium, chloride, potassium, magnesium, bicarbonate, calcium, phosphorus, total protein, albumin, alkaline phosphatase, glucose, total bilirubin, direct and indirect bilirubin, lactate dehydrogenase (LDH), cholesterol, uric acid, triglyceride levels, gamma glutamyl transpeptidase (GGT), AST, and ALT.

2) Exploratory Endpoint Laboratory Assessments (Baseline, Days 84 then every 84 days and EoT visit)

A 1 x 10 mL whole blood sample to assess vaccine-specific cytokine levels and in-vitro inhibition of tumor cell growth will be obtained from each patient at Days 0, 84 then every 84 days and at EoT visit. When vaccination with IMU-131 occurs, these samples will be taken prior to vaccination.

3) Phase 2 and Phase 2 Extension Immunologic Assessments

a) Humoral samples (Baseline, Days 21, 42, 63, 84, 126 then every 42 days and EoT visit)

A 1 x 10 mL whole blood sample for humoral immunity will be obtained from each patient at Days 0, 21, 42, 63, 84, 126 then every 42 days and at EoT visit. When vaccination with IMU-131 occurs, these samples will be taken prior to vaccination.

b) Cellular samples (Screening [Phase 2 Extension only], Baseline, Days 84 then every 84 days and EoT visit)

Collection of 40 mL blood sample will be performed for PBMC isolation and analysis of cellular parameters at Days 0, 84 then every 84 days and at EoT visit. When vaccination with IMU-131 occurs, these samples will be taken prior to vaccination.

During the Phase 2 Extension study, a Screening Visit collection of 40 mL blood sample for PBMC isolation and analysis of cellular parameters will be performed after enrolment eligibility including HER2 over-expression is confirmed.

Investigational Product: IMU-131
Protocol Identifier: IMU.ACS.001
Protocol Version: Protocol Global Amendment #5, 27 September 2023

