- H Cardiac assessment will be based on assessment of medical history, physical examination, 12-lead ECG results and evaluation LVEF by echocardiography or MUGA scan at Screening, Days 84 then every 84 days and at EoT visit.
- I No tumor biopsy is required if a previous pathology result or archival tissue is available confirming HER2/neu expression consistent with Inclusion Criteria #6.
- J Optional Day 84 and post-progression tumor biopsy (which may be provided at any time post progression).
- K Visit only for 'IMU-131 plus chemotherapy' group.
- L Record temperature 30min (+/- 10mins) after each IMU-131 vaccination.
- M Local laboratory testing. Safety lab samples can be drawn up to 72 hours before any on-study clinic visit.
- N A targeted, symptom directed physical examination may be performed at visits occurring after the Baseline Visit.
- O When progressive disease or withdrawal from study has been confirmed, EoT visit will be conducted at least 28 Days (+/- 7) after last dose of study medication. AEs to be checked at least 28 days after last study treatment per [Section 9.2: Reporting Period](#).
- P Phase 2 Extension only: Screening 40 mL cellular immunity blood sample after enrolment eligibility including HER2 over-expression is confirmed.
- Q Phase 2 only: Phase 2 Extension patients will no longer complete Post Treatment Follow Up Visits

Investigational Product: IMU-131
Protocol Identifier: IMU.ACS.001
Protocol Version: Protocol Global Amendment #5, 27 September 2023

R R End of trial is defined as 28 days post the last patient completing the end of treatment visit.

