- Record adverse events;
- Initiate chemotherapy cycle 1.

6.4.3. Phase 2 and Phase 2 Extension Week2/Day 14 (only for patients in IMU-131 plus chemotherapy cohorts)

The visit window for Day 14 is +/- 3 days of the scheduled visit. Day 14 procedures should be performed in the following order:

- Weight, and vital signs (blood pressure, temperature and heart rate);
- Urine pregnancy test (female);
- Administer IMU-131 vaccination;
- Record body temperature 30 (+/-10) minutes after vaccination;

Investigational Product: IMU-131
Protocol Identifier: IMU.ACS.001
Protocol Version: Protocol Global Amendment #5, 27 September 2023

- Record concomitant treatments;
- Record adverse events.

6.4.4. Phase 2 and Phase 2 Extension Week 3/Day 21

The visit window for Day 21 is +/- 3 days of the scheduled visit. Day 21 procedures should be performed in the following order:

- Blood sample for hematology and serum chemistry;
- Blood sample for humoral immunology;
- Weight, and vital signs (blood pressure, temperature and heart rate);
- Urine pregnancy test (female);
- Physical examination;
- Record concomitant treatments;
- Record adverse events;
- Initiate chemotherapy cycle 2.

6.4.5. Phase 2 and Phase 2 Extension Week 5/Day 35 (only for patients in IMU-131 plus chemotherapy cohorts)

The visit window for Day 35 is +/- 3 days of the scheduled visit. Day 35 procedures should be performed in the following order:

- Weight, and vital signs (blood pressure, temperature and heart rate);
- Urine pregnancy test (female);
- Administer IMU-131 vaccination;
- Record body temperature 30 (+/-10) minutes after vaccination;
- Record concomitant treatments;
- Record adverse events.

6.4.6. Phase 2 and Phase 2 Extension Week 6/Day 42

The visit window for Day 42 is +/- 3 days of the scheduled visit. Day 42 procedures should be performed in the following order:

- Blood sample for hematology and serum chemistry;
- Blood sample for humoral immunology;
- Weight, and vital signs (blood pressure, temperature and heart rate);
- Urine pregnancy test (female);
- Physical examination;
- Radiographic assessment;
- Record concomitant treatments;

Investigational Product: IMU-131
Protocol Identifier: IMU.ACS.001
Protocol Version: Protocol Global Amendment #5, 27 September 2023

- Record adverse events;
- Initiate chemotherapy cycle 3.

6.4.7. Phase 2 and Phase 2 Extension Week 9/Day 63

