10.5.1. Phase 2 Dose Escalation Definition of Dose-Limiting Toxicity (DLT)

A dose limiting toxicity (DLT) is defined as an IMU-131-related Grade 3 toxicity that cannot be resolved to a Grade 1 with appropriate therapy within 2 weeks, or a Grade 4 or greater toxicity graded by CTCAE v5.0, related to the IMU-131 vaccine.

In addition, after enrollment in Phase 2 dose escalation begins, the CRC will meet by teleconference as soon as feasible after any of the following occur to determine if the criteria for dose limiting toxicity (DLT) has been met:

- One or more patients experience a serious adverse reaction assessed as related to the vaccine by the investigator.
- One or more patients experience anaphylaxis.

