10.5.2. Phase 2 Dose Escalation

Between 3 - 6 patients will be enrolled in each Phase 2 dose escalation cohort for safety evaluation by CRC prior to next dose being opened to enrollment. The CRC will review data from one complete cycle of chemotherapy and 3 doses of IMU-131, for at least 3 patients in a dose cohort to authorize dose escalation. The DLT window is 35 days.

Dose escalation in Phase 2 will start at 100 μ g IMU-131, within a standard 3 + 3 scheme for determination of safety prior to opening enrollment to the 200 μ g IMU-131 dose cohort. A dose cohort must be reviewed by CRC for DLTs according to dose escalation decision rules before opening the next dosed cohort.

Either the 100 μ g or 200 μ g dose escalation cohort may be expanded up to 10 patients after CRC clearance of the 35-day DLT period.

Phase 2 Dose Escalation Decision Rules:

- If 0 out of 3 patients with treatment DLT at a given IMU-131 dose level, enter 3 patients at the next dose level;
- If ≥ 2 of 3 patients with treatment related DLT at a given dose level, dose escalation will be stopped. This dose level will be declared the maximally administered dose (highest dose administered). Three (3) additional patients will be entered at the next lower dose level if only 3 patients were treated previously at that dose;
- If 1 out of 3 patients with treatment related DLT at a given dose level, enter at least 3 more patients at this dose level. If 0 of these 3 patients experience treatment related DLT, proceed to the next dose level. If 1 or more of this group suffer treatment related DLT, then dose escalation is stopped, and this dose is declared the maximally administered dose. Three (3) additional patients may be entered at a dose between the current dose and the next lowest dose level, the exact dose of which will be determined by the CRC.

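### In the Extension, Day 21 is the only scheduled post-dose safety lab in the 35-day DLT window, so the schedule does not ensure that the 2-week Grade 3 criterion is observed before the CRC may clear a cohort

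*Protocol*

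**What the plan says.** Protocol 8.6 and Table 3 give one safety-lab schedule for Phase 2 and the Extension: "Safety Laboratory Assessments (Screening, Baseline, Days 21, 42, 63, 84, 105, 126 then every 42 days and EoT visit". Sections 6.4.3 and 6.4.5 list what is done at the Day 14 and Day 35 vaccination visits. Adverse events are recorded there, but no hematology or chemistry is drawn. Table 3, footnote M adds: "Safety lab samples can be drawn up to 72 hours before any on-study clinic visit".

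Section 10.5.2 states: "The DLT window is 35 days". Section 10.5.1 makes a DLT either "an IMU-131-related Grade 3 toxicity that cannot be resolved to a Grade 1 with appropriate therapy within 2 weeks" or any vaccine-related toxicity of Grade 4 or above, the latter with no condition on duration. Under 10.5 the CRC meets after a cohort has completed Day 35 and before the next cohort starts, and no latest day is set. Under 10.5.2, no DLT in 3 patients opens the next dose level, while 1 in 3 brings in at least 3 more patients at the same level.

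Phase 1b used the same 2-week criterion with a different schedule, given in Section 7.5: "Phase 1b Safety Laboratory Assessments (Screening, Days 0, 14, 35, 56, 77, 98, LTM visits".

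**The concern.** The DLT definition depends on laboratory information that the schedule largely does not collect inside the window. A Grade 3 value found on Day 21 reaches its 2-week point on Day 35. The patient attends that day, but no blood test is scheduled. A Grade 3 value that begins after Day 21 is first seen on a scheduled lab at Day 42, after the CRC may already have met. A related Grade 4 value that comes and goes between Day 0 and Day 21, or between Day 21 and Day 42, leaves no trace unless someone orders an extra test.

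Laboratory toxicity is a realistic route to a DLT here. Section 1.3 reports that the only two Phase 1b events rated as related, rather than possibly related, were Grade 2 hypoalbuminemia and Grade 3 hyponatremia in one patient, at doses of at most 50 µg. No DLT was reported. The Extension gives 100 and 200 µg. Section 9.1 collects adverse events through a general question, which will not reveal an abnormality without symptoms. Treatment-emergent Grade 3/4 laboratory abnormalities are also part of the Extension's primary endpoint (Section 2.2).

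Both kinds of miss lower the DLT count. In a 3-patient cohort, one uncounted DLT is the difference between entering 3 more patients and escalating.

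**Working it through.** The documents give no detection or lab-interval figure to reproduce. The check is arithmetic on the stated days.

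**Inputs**
- Scheduled labs: Day 0 (Baseline), Day 21, Day 42 (8.6, Table 3).
- Vaccinations: Days 0, 14 and 35 (5.2.3).
- Visit windows (Section 6.4): "The visit window for Day 21 is +/- 3 days of the scheduled visit"; "The visit window for Day 42 is +/- 3 days of the scheduled visit".
- Draw allowance: up to 3 days before the visit (Table 3, footnote M).
- DLT window: 35 days. Grade 3 criterion: 14 days.

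**1. Scheduled post-dose labs in the window.** The earliest permitted Day 42 draw is 42 − 3 − 3 = Day 36, which is past Day 35. Day 21 is therefore the only one under every permitted variation, and none in the window follows the Day 35 dose.

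**2. Gap from the Day 21 lab to the next.**
- Nominal: 42 − 21 = 21 days.
- Visit to visit: 39 − 24 = 15 to 45 − 18 = 27 days.
- Draw to draw: the Day 21 sample can fall on Days 15 to 24 and the Day 42 sample on Days 36 to 45. The gap is 36 − 24 = 12 to 45 − 15 = 30 days.
- In whole days there are 7 × 7 × 4 × 4 = 784 combinations of visit day and draw lead. In 15 of them (1.9%) the gap is 14 days or less. This counts combinations; it is not a probability that patients will follow them.

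**3. The 2-week point.** For a value found at the Day 21 visit it is Day 21 + 14 = Day 35 (range 32 to 38), with no lab scheduled. For onset after Day 21 it falls after Day 35, so the event cannot yet be classified when the window closes.

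**4. Share of abnormalities that a scheduled draw catches.** The documents give neither onset nor duration. Assume onset uniform over Days 0 to 35, nominal visit days, and detection only if a scheduled draw falls inside the episode. Each draw then covers the onset days in the d days before it, where d is the duration. The share caught is the covered onset days divided by 35.

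| Duration | Day 21 only | Days 21 and 42 | Phase 1b pattern (Days 14 and 35) |
|---|---|---|---|
| 7 days | 7/35 = 20% | 7/35 = 20% | 14/35 = 40% |
| 14 days | 14/35 = 40% | 21/35 = 60% | 28/35 = 80% |
| 21 days | 21/35 = 60% | 35/35 = 100% | 35/35 = 100% |

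**5. Phase 1b spacing, for comparison.** Its Day 14 and Day 35 visits also had windows of 3 days either way, so their gap is 32 − 17 = 15 to 38 − 11 = 27 days. This equals the Extension's visit-to-visit gap. The difference between the phases is one in-window post-dose draw against two.

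**The case against.** The strongest reply is that scheduled labs are not the only source of information. Unscheduled visits may include any protocol assessment (8.11). Adverse events are followed until resolved or stable, and the investigator must obtain enough information to determine the outcome (9.1). Potential liver-injury values call for re-evaluation, preferably within 48 hours (9.5.1). The CRC reviews all available safety data and may meet later than Day 35. A reader might infer that the 2-week criterion cannot be applied at all; these provisions show that it can. What they do not do is require it. Unscheduled visits are discretionary, AE follow-up sets no 14-day check, 9.5.1 covers liver signals only, and none of them finds a silent abnormality that no draw has picked up.

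Three other stronger readings also fail:
- That the gap to the next lab always exceeds 2 weeks. The 72-hour draw allowance permits 12 days, although gaps of 14 days or less are rare.
- That missing most short-lived abnormalities means missing most DLTs. A Grade 3 value that returns to Grade 1 within 2 weeks is not a DLT, so the 7-day figures bear only on related Grade 4 values. A 21-day Grade 3 episode with onset in the window is caught by Day 21 or Day 42 in every case, provided the CRC waits for Day 42.
- That the Extension spaces its labs more widely than Phase 1b did. The visit spacing is the same; what is lost is one draw.

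It is also fair to say that extra draws alone would not settle the matter. Phase 1b took blood before vaccination, so a Day 35 draw done the same way says nothing about the third dose. With visit windows of 3 days either way, it would follow the Day 21 visit by 32 − 24 = 8 to 38 − 18 = 20 days.

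**Conclusion.** The point holds in a limited form. The Extension schedule has one post-dose safety lab inside the DLT window, and the next comes nominally 21 days later. It therefore does not ensure that the protocol's own Grade 3 criterion is observed before the CRC may clear a cohort. The exposure is confined to short-lived related Grade 4 laboratory values and persistent related Grade 3 values arising after Day 21. Both errors run towards fewer counted DLTs and towards escalation.

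The one-lab finding and the 12-to-30-day range follow directly from the documents. The detection shares (20% and 40%, against 40% and 80% for the Phase 1b pattern) rest on assumed uniform onset, nominal visit days and scheduled labs only. They show the relative loss and do not predict how many DLTs will be missed. The sponsor should act on this, because the correction is cheap and the escalation decision can rest on 3 patients.

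**What to change.** Reconcile Table 3, Sections 6.4.3, 6.4.5 and 8.6 (when safety labs are drawn) with 10.5, 10.5.1 and 10.5.2 (the DLT definition, its window and when the CRC may meet). The aim is that the labs taken and the data the CRC reviews allow the stated definition to be evaluated. Two things need an explicit statement: how resolution of a Grade 3 laboratory value is to be observed against the 2-week criterion, and how the CRC treats a value whose 2 weeks are still running when the cohort completes Day 35.

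Phase 1b's hematology and chemistry draws at the Day 14 and Day 35 vaccination visits (6.2.3, 6.2.4, 7.5.1) are a precedent within this protocol. The exact timing and any re-check rule are for the sponsor's clinical team to set.

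The cost is at most a few extra local draws of about 10 mL, at visits that already take place, in up to 20 patients, plus a short amendment.
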